conjunctivitis found in the articles reviewed between patients treated with any drug vs patients treated with placebo. The Fleiss formula is used for case-control studies.

From the calculations made we can draw the following conclusions and recommendations. The average absolute efficacy found in the articles commented is almost 70% (69.8%) for patients treated with any medication and only 53.3% for patients treated with placebo (in this case vehicle was used as a placebo). According to the Fleiss formula for cases and controls, a sample of 147 cases per group assures us that if the differences that we are going to prove between the treatments is of that magnitude (69.8 %% vs 53.3%) or greater, we will have a 80% probability that the statistical test that we apply to evaluate the differences will be statistically significant (Power or power of the sample), and on the other hand, if the differences between the treatments were not of that magnitude (the differences were of lesser magnitude), when applying a statistical test on the results of a sample of 147 cases with minor differences to the ones presented, it will be not significant and the probability of this happening will be 0.95 (Reliability of the sample).

In summary, to prove differences in the absolute efficacy of two treatments in which one has almost 70% absolute efficacy and the other of only 53.3%, a sample of 147 cases per group will be necessary to have a reliability of 95% and a 80% power.

If instead of calculating the sample size with absolute efficiency we calculate it with the specific efficacy for specific bacteria, using the percentages that we obtained from the review of the articles published and that were 92.34% and 66.12% for patients treated with some medication and for those treated with placebo respectively, the sample according to the Fleiss formula for a 95% reliability and a power of 80% is 44 patients per group.

We can suggest that the minimum sample should be 50 eyes per treatment group and if possible, it would be desirable that the sample per group could reach 150 cases per group.

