ANNEX 1. Calculation of sample size.

Fórmula de Fleiss para el cálculo del tamaño de muestra para proporciones.
 "Statistical Methods for Rates and Proportions" 2a. Ed. Pp. 38-45 Wiley. 1981. EUA.
Casos y Controles.

r = Razón de: Controles : Casos = 1 : 1 1.00

P1 = Eficacia absoluta en el grupo tratado con algun medicamento. 0.6980

Q1 = 1 - P1 0.3020

P2 = Eficacia absoluta en el grupo tratado con placebo. 0.5330

Q2 = 1 - P2 0.4670

P = Proporción promedio ponderada de eficacia absoluta.

$$P = \frac{(P1 + r * P2)}{r + 1} 0.6155$$

Q = 1 - P 0.3845

α = Nivel de significancia o probabilidad de error tipo 1 0.050

$1-\alpha/2$ = Percentil bilateral para el nivel de significancia asignado 0.975

$Z_{1-\alpha/2}$ = $Z_{0.975}$ de la distribución normal estandarizada que deja un area de 0.975 a la izquierda. Implica una confiabilidad del 95% 1.960

β = Probabilidad de error tipo 2 0.200

$1-\beta$ = Percentil unilateral para la beta asignada 0.800

$Z_{1-\beta}$ = $Z_{0.80}$ de la distribución normal estandarizada que deja un area de 0.80 a la izquierda. Implica un poder del 80% 0.842

m' = Tamaño de muestra

$$m' = \frac{(z_{1-\alpha/2} \sqrt{(r+1) * P * Q} + z_{1-\beta} \sqrt{r * P1 * Q1 + P2 * Q2})^2}{r * (P2 - P1)^2}$$

$$m' = \frac{(1.960 \sqrt{(1.00+1) 0.62 * 0.38} + 0.842 \sqrt{1.00 * 0.70 * 0.30 + 0.53 * 0.47})^2}{1.00 (0.53 - 0.70)^2}$$

$$m' = 135.272$$

m = Tamaño de muestra corregido

$$m = 0.25 m' * \left\{ 1 + \sqrt{1 + \frac{2(r+1)}{m' * r * |P2 - P1|}} \right\}^2$$

$$m = 147 \quad \begin{array}{l} \text{Tamaño de muestra para el grupo de referencia (Controles): } m_1 = r * m \\ \text{Tamaño de muestra para el grupo de estudio (Casos): } m_2 = m \end{array} \quad \begin{array}{l} 147 \\ 147 \end{array}$$

Fórmula de Fleiss para el cálculo del tamaño de muestra para proporciones.
 "Statistical Methods for Rates and Proportions" 2a. Ed. Pp. 38-45 Wiley. 1981. EUA.
 Casos y Controles.

r = Razón de: Controles : Casos = 1 : 1 1.00

P1 = Eficacia específica en el grupo tratado con algun medicamento. 0.9234
Q1 = 1 - P1 0.0766

P2 = Eficacia específica en el grupo tratado con placebo. 0.6612
Q2 = 1 - P2 0.3388

P = Proporción promedio ponderada de eficacia específica

$$P = \frac{(P1 + r * P2)}{r + 1} 0.7923$$

Q = 1 - P 0.2077

α = Nivel de significancia o probabilidad de error tipo 1 0.050

$1-\alpha/2$ = Percentil bilateral para el nivel de significancia asignado 0.975

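### Section 23 gives 0.95 as the chance of non-significance for any difference below 16.5 points, but that figure is 1 minus alpha and applies only when the treatments do not differ

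*Combined protocol and SAP*

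**What the plan says.** Section 23 (Sample size) sizes a comparison of 69.8% against 53.3%, the pooled drug and placebo eradication rates from its literature review. It says 147 per group gives an 80% chance of significance if the difference is that large or larger. It then takes the opposite case, "if the differences between the treatments were not of that magnitude (the differences were of lesser magnitude", and says of a test on 147 cases that "it will be not significant and the probability of this happening will be 0.95". It calls this the reliability of the sample.

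Annex 1 gives the inputs: "Nivel de significancia o probabilidad de error tipo 1 0.050", taken two-sided ("Percentil bilateral para el nivel de significancia asignado 0.975"), and "Probabilidad de error tipo 2 0.200". It equates the 1.960 quantile with 95% reliability. A second calculation, 92.34% against 66.12%, gives 44 per group.

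The summary and Section 8 plan 60 eyes per group. The hypothesis in Sections 1 and 6.1 is non-inferiority to moxifloxacin and gatifloxacin. No margin, non-inferiority test or confidence-interval rule is stated. The paragraph on analysis sets names only a bivariate analysis in the per-protocol set.

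**The concern.** The condition attached to 0.95 is a difference smaller than planned, not a zero difference. That cannot sit beside the plan's own power statement. With 80% power at 16.5 points, 20% of trials are non-significant there, and this probability changes smoothly with the true difference. It cannot be 20% at 16.5 points and 95% just below.

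The sentence matters beyond its wording because it is the only text in the documents on what a non-significant result means. The trial aims to conclude that PRO-157 is as effective as two active controls. A reader who accepts the sentence would take non-significance as strong assurance that any difference is small, and the design does not give that assurance.

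**Working it through.** **Inputs (Annex 1).** "Eficacia absoluta en el grupo tratado con algun medicamento. 0.6980"; "Eficacia absoluta en el grupo tratado con placebo. 0.5330"; two-sided alpha 0.05 (z = 1.960); power 80% (z = 0.842); allocation 1:1. Planned group size of 60 eyes from the summary and Section 8.

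**Reproducing the plan's figures.** The mean rate is (0.698 + 0.533)/2 = 0.6155.

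- m′ = [1.960·√(2·0.6155·0.3845) + 0.842·√(0.698·0.302 + 0.533·0.467)]² / 0.165² = 135.27. The plan has 135.272.
- With continuity correction: m = 0.25·135.27·[1 + √(1 + 4/(135.27·0.165))]² = 147.14. The plan has 147.
- The second contrast, 0.9234 against 0.6612, gives 36.37 and then 43.67, so 44, as stated.

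**Probability of non-significance at a true difference d.** For the pooled two-proportion z-test with n per group:

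- critical difference c = 1.960·√(2P̄Q̄/n), plus 1/n with the continuity correction;
- SE₁ = √((P₁Q₁ + P₂Q₂)/n);
- P(non-significant) = Φ((c − d)/SE₁) − Φ((−c − d)/SE₁).

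The documents do not say which rate stays fixed as d shrinks. I hold P₁ at 0.698 and set P₂ = 0.698 − d.

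Example, n = 147, d = 0.10, corrected: P̄ = 0.648, so c = 1.960·0.05571 + 1/147 = 0.1160; SE₁ = 0.0554; (0.1160 − 0.10)/0.0554 = 0.289; Φ = 0.61.

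| True difference (points) | Continuity-corrected, n = 147 | Uncorrected, n = 147 | Section 23 |
|---|---|---|---|
| 0 | 0.96 | 0.95 | 0.95 |
| 5 | 0.88 | 0.85 | 0.95 |
| 10 | 0.61 | 0.57 | 0.95 |
| 12 | 0.48 | 0.43 | 0.95 |
| 15 | 0.28 | 0.24 | 0.95 |
| 16.5 | 0.20 | 0.17 | 0.20 (1 − power) |

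Holding the lower rate at 53.3% instead moves these values by about 2 points at most (uncorrected: 0.86, 0.59, 0.45 and 0.25 at 5, 10, 12 and 15 points).

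**If the sentence means observed differences.** At n = 147 with a mean rate of 0.6155, the smallest significant observed gap is 1.960·√(2·0.6155·0.3845/147) = 11.1 points (11.8 corrected). Observed gaps between there and 16.5 points would be significant, so this reading fails too.

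**At the planned 60 eyes per group, for both sizing contrasts.**

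- 69.8% against 53.3%: c = 0.1741 (0.1908 corrected), SE₁ = 0.0875, d = 0.165. P(non-significant) = 0.54 (0.62), so power is 46% (38% corrected).
- 92.34% against 66.12%: c = 0.1452 (0.1618 corrected), SE₁ = 0.0701, d = 0.2622. P(non-significant) = 0.05 (0.08), so power is 95% (92% corrected).

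**The case against.** The best defence is that this is a loose gloss on a correctly defined quantity. Annex 1 labels alpha as the type I error probability, both sample sizes reproduce, and correcting the sentence alters no sample size, endpoint, analysis set or test. All of that stands, and a reader should not infer that the sample-size arithmetic is wrong.

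A second tempting inference is that the plan intends to read non-significance as equivalence. The documents do not say so. Section 23 speaks of proving differences, the hypothesis is worded as non-inferiority, and no decision rule uses the 0.95. What can be said is narrower: with no margin or interval rule anywhere, nothing in the text prevents that reading, and this sentence invites it.

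A third is that 60 eyes per group leave a non-significant result the likelier outcome whatever is true. That holds for 69.8% against 53.3%, for which the plan itself asks for 147. It does not hold for 92.34% against 66.12%, the contrast behind the lower recommended size, where power at 60 is above 90% on either basis.

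It can also be said that 0.95 is nearly right for very small differences. That is true up to about 2 points (0.93 uncorrected, 0.95 corrected). The sentence covers everything up to 16.5.

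**Conclusion.** The sentence is wrong as written: it states an operating characteristic that the design does not have. The nominal 0.95 belongs to zero difference. At 147 per group the probability of non-significance falls to about 61% at 10 points and 28% at 15 on the plan's continuity-corrected basis, and the uncorrected figures are 3 to 5 points lower. The size of the discrepancy rests on the normal approximation, independent eyes and one rate held at 69.8%. The conclusion does not depend on any of these choices, because the plan's own 80% power already contradicts the sentence just below 16.5 points.

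This is an error of interpretation that should be corrected, not a calculation error. It bears on the conclusions because the trial seeks a non-inferiority claim and gives no other guidance on a non-significant result.

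**What to change.** In Section 23:

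1. Replace the sentence with: 0.95 is the nominal probability of a non-significant result only if the treatments do not differ; it falls as the true difference grows, to 20% at 16.5 points with 147 per group.
2. State the power at 60 eyes per group for both contrasts: 46% (38% continuity-corrected) for 69.8% against 53.3%, and 95% (92% corrected) for 92.34% against 66.12%.
3. Add that a non-significant difference test will not be taken as evidence of similarity or non-inferiority, and that each PRO-157 versus control difference will be reported with its 95% confidence interval.

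The interval alone supports estimation. A non-inferiority conclusion would also need a pre-specified margin, which the documents do not give. The cost is a few sentences; the calculations giving 147 and 44 and the planned 60 eyes are untouched.

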ANNEX 1. Calculation of sample size.

Fórmula de Fleiss para el cálculo del tamaño de muestra para proporciones.
 "Statistical Methods for Rates and Proportions" 2a. Ed. Pp. 38-45 Wiley. 1981. EUA.
Casos y Controles.

r = Razón de: Controles : Casos = 1 : 1 1.00

P1 = Eficacia absoluta en el grupo tratado con algun medicamento. 0.6980

Q1 = 1 - P1 0.3020

P2 = Eficacia absoluta en el grupo tratado con placebo. 0.5330

Q2 = 1 - P2 0.4670

P = Proporción promedio ponderada de eficacia absoluta.

$$P = \frac{(P1 + r * P2)}{r + 1} 0.6155$$

Q = 1 - P 0.3845

α = Nivel de significancia o probabilidad de error tipo 1 0.050

$1-\alpha/2$ = Percentil bilateral para el nivel de significancia asignado 0.975

$Z_{1-\alpha/2}$ = $Z_{0.975}$ de la distribución normal estandarizada que deja un area de 0.975 a la izquierda. Implica una confiabilidad del 95% 1.960

β = Probabilidad de error tipo 2 0.200

$1-\beta$ = Percentil unilateral para la beta asignada 0.800

$Z_{1-\beta}$ = $Z_{0.80}$ de la distribución normal estandarizada que deja un area de 0.80 a la izquierda. Implica un poder del 80% 0.842

m' = Tamaño de muestra

$$m' = \frac{(z_{1-\alpha/2} \sqrt{(r+1) * P * Q} + z_{1-\beta} \sqrt{r * P1 * Q1 + P2 * Q2})^2}{r * (P2 - P1)^2}$$

$$m' = \frac{(1.960 \sqrt{(1.00+1) 0.62 * 0.38} + 0.842 \sqrt{1.00 * 0.70 * 0.30 + 0.53 * 0.47})^2}{1.00 (0.53 - 0.70)^2}$$

$$m' = 135.272$$

m = Tamaño de muestra corregido

$$m = 0.25 m' * \left\{ 1 + \sqrt{1 + \frac{2(r+1)}{m' * r * |P2 - P1|}} \right\}^2$$

$$m = 147 \quad \begin{array}{l} \text{Tamaño de muestra para el grupo de referencia (Controles): } m_1 = r * m \\ \text{Tamaño de muestra para el grupo de estudio (Casos): } m_2 = m \end{array} \quad \begin{array}{l} 147 \\ 147 \end{array}$$

Fórmula de Fleiss para el cálculo del tamaño de muestra para proporciones.
 "Statistical Methods for Rates and Proportions" 2a. Ed. Pp. 38-45 Wiley. 1981. EUA.
 Casos y Controles.

r = Razón de: Controles : Casos = 1 : 1 1.00

P1 = Eficacia específica en el grupo tratado con algun medicamento. 0.9234
Q1 = 1 - P1 0.0766

P2 = Eficacia específica en el grupo tratado con placebo. 0.6612
Q2 = 1 - P2 0.3388

P = Proporción promedio ponderada de eficacia específica

$$P = \frac{(P1 + r * P2)}{r + 1} 0.7923$$

Q = 1 - P 0.2077

α = Nivel de significancia o probabilidad de error tipo 1 0.050

$1-\alpha/2$ = Percentil bilateral para el nivel de significancia asignado 0.975

$Z_{1-\alpha/2} = Z_{0.975}$ de la distribución normal estandarizada que deja un area de 0.975 a la izquierda. Implica una confiabilidad del 95% 1.960

β = Probabilidad de error tipo 2 0.200

$1-\beta$ = Percentil unilateral para la beta asignada 0.800

$Z_{1-\beta} = Z_{0.80}$ de la distribución normal estandarizada que deja un area de 0.80 a la izquierda. Implica un poder del 80% 0.842

m' = Tamaño de muestra

$$m' = \frac{(z_{1-\alpha/2} \sqrt{(r + 1) * P * Q} + z_{1-\beta} \sqrt{r * P1 * Q1 + P2 * Q2})^2}{r * (P2 - P1)^2}$$

$$m' = \frac{(1.960 \sqrt{(1.00+1) 0.79 * 0.21} + 0.842 \sqrt{1.00 * 0.92 * 0.08 + 0.66 * 0.34})^2}{1.00 (0.66 - 0.92)^2}$$

$$m' = 36.373$$

m = Tamaño de muestra corregido

$$m = 0.25 m' * \left[1 + \sqrt{1 + \frac{2(r + 1)}{m' * r * |P2 - P1|}} \right]^2$$

$$m = 44 \quad \begin{array}{l} \text{Tamaño de muestra para el grupo de referencia (Controles): } m_1 = r * m \\ \text{Tamaño de muestra para el grupo de estudio (Casos): } m_2 = m \end{array} \quad \begin{array}{l} 44 \\ 44 \end{array}$$

Analyzed data set

The data will be analyzed in two groups, one will be made up of the population evaluable by Intention to Treat (ITT) in which each of the variables is described, the ITT population will be constituted by all the recruited subjects who have received at least one dose of study treatment.

Others will be the evaluable population Per Protocol (PP) which is the subset of ITT composed of all subjects without any major deviation from the protocol, in which the bivariate analysis will be performed.

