7 STUDY DESIGN

7.1 Point or limit points

Criteria for the evaluation.

Efficacy measurements:

Main efficacy criterion

Efficacy will be determined by taking cultures of the lower conjunctival cul-de-sac background quantifying (colony-forming units) and identifying genus and basal and final microbial species.

It will be determined as effective if there is a reduction in the number or species of bacterial flora comparing the basal culture against the end between the five different groups of patients and / or if there is a reduction or absence of the following specific signs and symptoms: burning, tearing, Foreign body sensation, pruritus, photophobia, conjunctival hyperemia, chemosis, palpebral edema and secretion, membranes and / or pseudomembranes when comparing the study medication versus Moxifloxacin and versus Gatifloxacin from baseline to final visit.

Efficiency parameters

- The effectiveness of the drug will be evaluated by means of:

1. Clinical referral

2. Microbiological remission

Clinical remission will be evaluated by means of the signs and symptoms that the patient presents at the beginning and at the end of the study.

Variable	Operationalization	Measurement scale	Value
Secretion	Dependent Qualitative ordinal	Absent Present	Must be recorded as absent in 95% of the subjects evaluated
Conjunctival hyperemia	Dependent Qualitative ordinal	Absent Mild Moderate Severe	You must comply with the following: • Absent \geq 95.0% • Mild \leq 5.0% • Moderate \leq 2.5% Severe \leq 1.0%
Chemosis	Dependent Qualitative ordinal	Absent Present	Must be recorded as absent in 95% of the subjects evaluated
Eyelid edema	Dependent Qualitative ordinal	Absent Present	Must be recorded as absent in 95% of the subjects evaluated
Corneal epithelial defects	Dependent Qualitative ordinal	Affected area, percentage	Percentage of affected area less than 95%

The microbiological remission will be evaluated by means of the culture taken from the conjunctival sac fundus.

Variable	Operationalization	Measurement scale	Value
Culture	Dependent Discrete quantitative	UFC * / ml Eradication Reduction Proliferation	Must be recorded as absent in 95% of the subjects evaluated

* Colony forming units

The drugs under study will be considered effective if the patient has any of the following:

1. Clinical remission + Microbiological remission.
2. Clinical referral.
3. Microbiological remission.

Security measurements:

Adverse events and visual capacity.

Evaluation parameters

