- Any complication or lack of control that the doctor considers should be treated differently.

- **Elimination Criteria**

- Clinicians:

a. Any complication or lack of control that the doctor considers should be treated differently. The following points should be considered:

i. The no improvement of the initial clinical signs and symptoms.

ii. Diagnosis added or different to that of acute bacterial conjunctivitis.

iii. Use other medications outside the study.

b. * It is reiterated that they are minimum parameters to be considered, any other case in which the investigator considers necessary the elimination of the patient and suspension of the treatment must be informed and evaluated by the sponsor.

- For the sponsor:

- a. By its will, it will not have penalties, nor will it lose benefits to those that it already has right.
- b. For the total term of the scheduled visits in the clinical study.
- c. For a serious adverse event related to the medication that endangers your health.
- d. Why the medication does not work at the doctor's discretion.

and. Why, by sponsor's decision, the study ends earlier.

In case of withdrawal for any of these reasons or any other at the discretion of your doctor, you will be prescribed again the medication of which you were already a user or any other that is of benefit for your best treatment.

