15.3 Criteria for the premature withdrawal of the subject

Criteria for premature withdrawal

The following criteria will cause a mandatory withdrawal from the study:

The reasons for a patient leaving the study prematurely may be the following:

- Subject's decision. The patient who wishes to leave the study for any reason can do so at any time, but must inform the researcher. In all cases, the investigator should attempt to establish contact with the patient as soon as possible for a final evaluation in order to:
 - Document the patient's decision in clinical notes,
 - Obtain the reason (s) for the exit and write them down in the FRC exit format,
 - Evaluate the patient's clinical status,
 - If necessary, take the appropriate therapeutic measures: management of an adverse event.

In case of failure of all these attempts to contact the patient, the investigator may declare "loss of follow-up" of the patient. The investigator will document all the attempts in the corresponding medical file.

- Decision of the investigator. Especially if an adverse event occurs and the researcher considers that this may threaten the patient's health, or if an important disease occurs that requires the prescription of a medication incompatible with the objective of the study.
- Need for another treatment according to the criteria of the Medical Investigator who will have to document it well in his notes.
- Pregnancy (see procedure in Appendix 2)
- Any deviation to the protocol that affects the patient's safety.
- In all cases, the available data will be saved for the safety analysis (population evaluable by intention to treat).

Process

Whatever the reason for the premature discontinuation of the study treatment, the investigator should immediately inform Laboratorios Sophia S.A. of C.V. and the patient must return the rest of the study treatments to the center.

In case of premature withdrawal of treatment, the investigator should record the reason (s), the exact date of the premature discontinuation of the treatment in the source document and in FRC. If more than one reason is given, the investigator must indicate the main reason.

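### The bivariate analysis is assigned to the per-protocol set only, with major deviation undefined and no efficacy rule for eliminated patients, so the non-inferiority comparison could lose failures unchecked

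*Combined protocol and SAP*

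**What the plan says.** The paragraph on analysed data sets at the end of Section 23 names two sets. The first is the "population evaluable by Intention to Treat (ITT) in which each of the variables is described"; it holds every recruited subject who received at least one dose. The second is the PP set, a subset of ITT: "all subjects without any major deviation from the protocol, in which the bivariate analysis will be performed". The bivariate analysis is not described further. The phrase major deviation occurs nowhere else and is not defined.

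Section 7.1 plans an efficacy judgement by "comparing the basal culture against the end between the five different groups of patients" and by signs and symptoms, but names no analysis set. It counts a patient as a success with clinical remission, microbiological remission, or both. Section 6.1 frames the hypothesis as non-inferiority to moxifloxacin and gatifloxacin. No margin is stated.

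Several rules let a patient leave early for reasons tied to outcome:

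- Section 15.2, elimination criteria: "The no improvement of the initial clinical signs and symptoms", "Diagnosis added or different to that of acute bacterial conjunctivitis", use of other medication, and "Why the medication does not work". The same list also contains ordinary completion: "For the total term of the scheduled visits in the clinical study".
- Section 15.3, premature withdrawal: "Need for another treatment according to the criteria of the Medical Investigator". Reasons for exit are recorded, and available data are kept for the safety analysis in ITT.
- Section 16.3: removal if a prohibited treatment becomes necessary.

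Sections 9 and 16.5 require adherence above 80%, without linking this to the PP set. Table 2 schedules signs and symptoms at a discontinuation visit, but cultures only on days 1 and 8.

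**The concern.** A PP analysis is a normal part of a non-inferiority trial. The difficulty is that it is the only comparative analysis the plan names, and its membership is left open. If patients stopped because treatment failed also drop out of PP, success rates rise in every arm and a real deficit of the test product can look smaller. If such losses differ between arms, the bias can go either way. With ITT used only for description, no planned comparison would reveal this. No table of eliminations by arm and reason is planned either, although the reasons are collected.

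**Working it through.** **Can failures leave PP under the text?** The plan does not say that elimination is a major deviation, nor that it is not. One plausible route is adherence. The plan does not give the denominator; measured against the full 7-day course:

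- stopped at the day 3 visit: at most 3/7 = 42.9%
- stopped one day later, within the window: 4/7 = 57.1%
- five full days: 5/7 = 71.4%
- six full days: 6/7 = 85.7%

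If adherence of 80% or less were treated as a major deviation, anyone stopped for non-improvement after five days or fewer would leave PP.

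**Inputs.** The 60 eyes per group come from the summary and Section 8. The control success of 69.8% is the Annex 1 rate for absolute efficacy on drug, the mean of the three active rates: (74.53 + 76.92 + 57.96)/3 = 69.80. Annex 1's own sample sizes reproduce (147.2 against a stated 147; 43.7, rounded up to the stated 44), so no stated figure is in error here. The rest is assumed: margins M of 10, 15 and 20 points, a true deficit equal to M, independent eyes, random removal of a fraction f of failures, and every removed eye a failure. The test is a one-sided 2.5% unpooled Wald limit.

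**Direction.** The PP success rate is g(p) = p / [p + (1 − p)(1 − f)], with slope g′(p) = (1 − f)/(1 − f + fp)². For p ≥ 0.5 the slope is below 1 for every f > 0, so equal removal shrinks the difference. Example with f = 0.25:

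- control: 0.698/(0.698 + 0.302 × 0.75) = 0.755
- test: 0.598/(0.598 + 0.402 × 0.75) = 0.665
- the 10.0-point deficit becomes 9.0, with 60 × 0.302 × 0.25 = 4.5 control eyes removed

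**False non-inferiority at the margin (exact enumeration).**

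| Failures removed, test / control | PP deficit, points (M = 10 / 15 / 20) | Rate, % (M = 10 / 15 / 20) |
|---|---|---|
| none | 10.0 / 15.0 / 20.0 | 2.55 / 2.43 / 2.43 |
| 10% / 10% | 9.7 / 14.6 / 19.5 | 2.86 / 2.85 / 2.76 |
| 25% / 25% | 9.0 / 13.7 / 18.6 | 3.45 / 3.62 / 3.65 |
| 25% / 10% | 5.5 / 10.2 / 15.0 | 7.90 / 8.08 / 8.04 |
| 10% / 25% | 13.2 / 18.1 / 23.1 | 1.04 / 1.04 / 1.02 |

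Equal removal of half of all failures, by simulation, gives 5.5 to 7.4%.

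**ITT has its own bias.** Entry is on clinical suspicion (Section 15.1), so some non-improvers may not have bacterial disease. If a share q of eyes in each arm are such failures, the deficit becomes M(1 − q). The false non-inferiority rate is then 3.34 / 3.79 / 4.25% for q = 10% and 4.44 / 5.52 / 6.75% for q = 20%. Neither set is safe alone.

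**Power if both sets must agree (simulation).** With truly equal arms and 10% of failures removed from each, PP alone has about 23 / 44 / 67% power for the three margins, and both together about 20 / 40 / 64%. With 10% non-bacterial failures per arm as well, the fall is from 21 / 41 / 63% to 15 / 32 / 55%.

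**The case against.** A reader might infer that the plan excludes treatment failures from the efficacy comparison, or that it rules out a comparative ITT analysis. The documents support neither. Three unstated steps are needed: that bivariate analysis means the between-group test, that elimination or low adherence is a major deviation, and that those removed are failures. The term is used once, in translated text. Elimination cannot in itself mean exclusion, because the same list includes ordinary completion. An ITT comparison is not forbidden; none is assigned. These points stand, and they limit the claim to what the text permits. If bivariate means something else, the non-inferiority comparison has no assigned set at all, and clarification is still needed.

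The third step is also weakened by Section 7.1. A patient stopped for lack of clinical improvement may still have microbiological remission and so be a success. Counting all such patients as failures would change the endpoint, and the fix below avoids that. Likewise, 69.8% is a culture-eradication rate used to illustrate a broader composite.

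A reader might also take 8% as the expected error rate. It needs removal of 25% against 10%, for which the documents give no basis, and the reverse pattern is conservative. Equal removal of up to a quarter of failures has little effect.

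Finally, requiring both sets to agree is one reasonable convention, not something the documents demand, and it costs power in a study with 60 eyes per arm.

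**Conclusion.** The point holds as a gap that should be closed. Section 23 assigns description to ITT and the bivariate analysis to PP, leaves major deviation undefined, and no section says how patients stopped for non-improvement, lack of effect or need of other treatment count for efficacy. That these omissions exist is clear from the text; that failures would actually be lost is a possibility.

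The size of any bias cannot be derived without a margin and elimination rates. Under the assumptions above, it is about one percentage point of false non-inferiority when a quarter of failures leave both arms. It becomes large with removal that differs by arm, in either direction, or with equal removal well beyond a quarter.

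**What to change.** In Section 23:

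1. Perform and report the between-group comparison in ITT (all dosed patients) as well as PP, and require the two to be consistent before non-inferiority is claimed.
2. In ITT, apply the Section 7.1 endpoint to eliminated or withdrawn patients using whatever assessments exist. Count as failures those stopped for non-improvement, lack of effect or need of other anti-infective treatment when neither clinical nor microbiological remission is documented, including when there is no final culture. A documented microbiological remission keeps its Section 7.1 status.
3. Fix the PP exclusions before unmasking. State that stopping for lack of efficacy, or low adherence caused only by that stop, is not a major deviation.
4. Tabulate eliminations by arm and reason, and add a sensitivity analysis in patients with a positive baseline culture, which is already sampled before treatment.

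The clinical elimination rules stay as they are, and no visits or samples are added.

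The cost is SAP wording, one more comparison, one table and one sensitivity analysis. Observed success rates will be lower in ITT than in PP, and non-bacterial cases may dilute differences there; agreement with PP and the culture-positive analysis are meant to expose this. Requiring agreement costs roughly 3 to 5 points of power under the illustration, and about 6 to 9 points if 10% of eyes per arm are non-bacterial failures.
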